6.10 HIV Result Management

For each of the samples processed, the result can be reactive, non-reactive or no result/indeterminate. The results management will be shared between UCLH-TDL and CNWL:

1. In line with standard practice in most NHS sexual health clinics, negative results will be delivered by text message. UCLH-TDL will be responsible for the delivery of these messages. If a participant has only provided alternative contact means (landline or email) then UCLH will notify a named senior Health Advisor at CNWL who will assume responsibility for result notification as per clinic practice.
2. If consent to notify the GP has been provided (an option only applicable to those recruited via General practice) then the study manager will be responsible for informing the GP of negative results via secure email or registered address.
3. UCLH-TDL will let the senior study manager and CNWL know about any reactive results by secure encrypted email. Please note that at this stage, the names of participants with reactive samples are unknown to all parties as only initials are required with SSK return.
4. The Health Advisor at CNWL will use this information to retrieve personal information from the UCL Data Safe Haven (IDHS) to be able to link the sample to an individual. The Health Advisor at CNWL will retrieve the full name and contact details of the participant, and whether consent has been obtained to notify the GP.
5. The study manager will phone the Health Advisor to confirm access of test result and personal details.
6. The named CNWL Health Advisor will contact the participant by phone call and inform them of the reactive result and need for confirmatory testing. If consent is obtained from the participant they will arrange linkage into appropriate local services for confirmatory testing. Postcode data will be used by the Health advisor prior to contact to identify appropriate local services for any one participant. This will all be done without disclosure of participant details.

7. The Health Advisor will have follow up phone contact with all participants with a reactive result to ensure linkage to care has occurred. This will also provide an opportunity to identify any unexpected consequences of the testing process.
8. The Health Advisor will be responsible for completing the Pathways into care outcome measures CRF (appendix 10), this will involve follow up phone calls to HIV services and the participant to ensure linkage to care has occurred. This information will be directly entered into the IDHS using the secure UCL portal. They will also be responsible for notifying the GP of the result where consent has been provided; this option will only apply to those recruited through General Practice.
9. If the result is indeterminate, UCLH-TDL will highlight this result in the CSV file of results sent to the study Manager. The study manager will retrieve personal details from the IDHS database and pass these onto the clinic. One of the Health Advisors from the clinic will inform the participants of the indeterminate result and request permission for the study team to send them another kit or for them to attend an alternative testing venue. The Health Advisor will be responsible for completing the Pathways to care outcome measures CRF (appendix 10) again using the secure UCL portal to the IDHS.

6.11 HAUS Process Evaluation Plan

HAUS Process Evaluation Flowchart Key

Items in **BLUE** are key Phase II components

Items in **PURPLE** are process evaluation data collection points

Item in **BROWN** is outcome evaluation data which will also have implications for process evaluation

6.11.1 Study Diaries

The process evaluation incorporates information right from the start of Phase II planning. Using a standardised template format, the research team will routinely record decision making contributing to distributor selection, responses from potential distributors, rationales for inclusion / exclusion etc (see appendix 11). This will enable the process evaluation to capture the elements leading up to the start of distributor training and fieldwork.

6.11.2 Training Evaluation

At the training events, participants will be asked to complete a before / after survey assessing existing capacity and need with regard to approaching and persuading Black African people to use HIV self-sampling kits. The evaluation will focus on the extent to which the training meets its stated aims.

6.11.3 Fieldwork process evaluation

A. Screening and recruitment logs

Distributors will be asked to complete a daily screening and recruitment log. This will be completed throughout the day, capturing: basic information about potential participants approached (DOB, initials, Country of Birth/ gender) as well as refusals, reasons for refusal when known, and acceptances. This will assist in monitoring progress and help enable early intervention if further support in recruitment is required.

B. Distributor logs

Distributors will also be asked to complete a weekly log to monitor progress and detect problems with recruitment (see appendix 12). They will be asked to rate how they felt about the experience of undertaking targeting, recruitment, consent, fielding questions and use of behaviour change techniques to support uptake. These will be completed online, and will serve a dual purpose in the study. Firstly, it will be used to monitor progress and detect problems. Secondly, this information will be utilised for the purposes of the process evaluation.

C. Site Visits

A minimum of two site visits will be undertaken in each city to describe some of the environments and circumstances in which the intervention is being delivered. Observation templates will be completed which identify: special and temporal features which may facilitate or hinder the intervention, characteristics of the population and the nature of distributor targeting within this context, etc. The purpose of these visits is to ensure some enhanced awareness of distributor type issues and contexts, rather than trying to ascertain distributor behaviours and/or quality in each and every site. These site visits are distinct from routine site visits that will occur for study set up procedures or to support recruitment.

D. Data flow

We will monitor the speed and success of data flow through all elements of Phase II. Potential data bottlenecks will be identified and resolved at an early stage, and monitoring will help us to assess intervention feasibility.

E. Support queries and responses

Any contact made with project manager or other core team members by distributors, potential participants or study participants will be logged, as will the response given and action taken. Standard telephone summaries will be maintained by the project manager.

F. Distributor focus groups

Toward the end of the recruitment period, focus group discussions will be undertaken within CBO and GP settings in both Glasgow and London. Distributors and their managers will be invited to take part in groups held on each study site, and the focus will be on: acceptability of the intervention, distributors' experience of undertaking targeting, recruitment and consenting procedures, fielding questions, and using behavioural change techniques to support uptake (see appendix 15 for topic guide). Groups will also discuss future feasibility and any recommended changes, and consideration of targeting similar populations in other cities. The groups will be recorded, and a second facilitator will take notes throughout. Annotations will form the basis of analysis, with recordings providing backup where needed. Written consent (appendix 16) will be obtained from all those participating in the distributor focus group discussion.

G. Outcomes interviews with study participants

The outcomes interviews with study participants are described in detail in section 6.9.2. In addition to elaborating on outcomes indicators, we anticipate that a number of issues related to

intervention and study process will arise throughout these interviews that will be important to capture as a part of the process evaluation.

6.12 Subject Withdrawal

All participants will be informed during the consent process that they can withdraw from the study at any time and that this will not affect the standard of care that they receive from the organisations/care they are accessing. Should the participant request to be withdrawn from the study then they will have two options: 1. Withdraw from the study, and not be approached for further information. Samples and data already obtained however may still be retained and used. And 2: Participant requests no further contact, and for their samples and data to be destroyed.

Nevertheless, essential patient information, the sample and test result will be retained by the NHS if a consented participant returns a SSK that has already been processed before withdrawal. This information will not be destroyed even if the subject decides to withdraw from the research component of the study.

6.13 End of Study Definition

The end of the study will be when the final analysis of both the qualitative and quantitative data has been performed.

7. Statistical Considerations

7.1 Sample size calculation

Current HIV SSK projects in the UK, which primarily target men who have sex with men (MSM) online, have achieved return rates in the region of 60% (4, 23, 24). Given that in the UK HIV testing rates tend to be lower in Black African communities compared to MSM we have assumed a return rate of 50%. Distribution of a total of 600 kits per setting would enable a precision rate of at least $\pm 4.0\%$, and distribution of a total of 380 kits per setting would enable a precision rate of at least $\pm 5.0\%$ should the return rate be lower or higher with a fixed sample size the size of the standard error will be smaller and the resulting confidence intervals narrower.

We will have SSK distribution in both Glasgow and London however there will be more kits distributed in London than in Glasgow because London has a larger population of Black Africans and the recruitment is limited in Glasgow to primary care only. As such we will distribute 600 SSK in each site in London and 380 in via GP practice nurses in Glasgow. Although the power of the study (as reflected in the width of the confidence intervals around the parameter of interest)

increases as the response rate moves away from 50% due to the properties of the binomial distribution, the increase in power for plausible response rates is somewhat modest.

The study is driven by those subjects who engage with existing services provided by PNs and CWs. We will describe the characteristics of subjects who are recruited, alongside a minimum data set for those subjects who are eligible but elect not to take part in the study. Further, we will develop prognostic models to examine the extent to which participants with different characteristics achieve the primary outcome. The exact parameterisation of this model will be pre-specified with the project team prior to data base lock, and the maximum number of 'questions' asked will be derived from the available degrees of freedom such that they will not exceed the smaller of the events or non-events divided by 10, that way militating the risk of over-fitting. We will examine the functional form of continuous variables such as age, and use a conservative strategy to select from pre-specified transformation or restricted cubic splines, with the switch to a more complex functional form driven by observed significant improvement in model fit as derived by the Akaike Information Criterion. While necessarily exploratory given the primary aim of the study, the prognostic model will help us to develop an understanding of important characteristics such as age and gender in the probability that completed test kits will be returned.

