5. Build sustainable relationships with community service providers willing to distribute and evaluate SSKs as an add-on to existing services.
6. Monitor ability to trace participants with reactive results, confirmatory testing and linkage into specialist care.
7. Determine sample size parameters and control population for a phase III trial offering HIV SSK.
8. Determine the cost per person kit distributed and cost per HIV diagnosis per setting.

9. Assess the feasibility of collecting data for a lifetime cost-effectiveness model alongside a Phase III trial.
10. Assess feasibility, and if appropriate the optimal trial design for future phase III evaluation.

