6.4 Intervention Design

The HAUS study seeks to develop and test an intervention of targeted distribution of self-sampling kits (SSK) for HIV testing within health care and community services to determine if this will increase HIV testing in African communities. The kits will be distributed by Practice Nurses (PN) in GP clinics in both Glasgow and London, and in London also by Community Workers (CW) from community organisations as a part of their outreach. Those who distribute the kits will be supported by a programme of training on the delivery of the intervention and research governance. All procedures will also be outlined in an intervention manual (including data collection, result management and linkage to care- see appendix 6). Scripts will be provided to the distributors (see section 6.7) to facilitate study engagement. These resources will help the PNs/CWs to identify and approach black Africans, recruit participants to the study, explain the kit testing and study processes, collect baseline data and complete uptake and refusal logs. Participants will be given a plain language information sheet about the study and a description of how to take the sample (including a link to an online video of someone completing the test) and return the sample. UCLH will provide the clinical oversight for the study. They will subcontract The Doctors Laboratory (TDL) to process the samples. Samples will be sent to TDL via Royal Mail and negative results will be delivered directly to participants via text message (or phone call if only a landline number is provided). Management of all reactive results will be provided by Central and North West London (CNWL) NHS Trust as part of their existing clinical systems. Where a sample is reactive, the individual will be directly contacted by telephone by an experienced member of their clinical team to discuss the results, their implications and to make a clear referral for confirmation testing and care.

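### The stated precision of ±4.0% and ±5.0% holds only if kits are independent, an assumption Section 7.1 does not state and delivery within practices and organisations makes doubtful

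*Protocol*

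**What the plan says.** Protocol Section 7.1 sizes the study on the precision of the primary outcome, the kit return rate (Section 5.4). It takes a single planning value, "we have assumed a return rate of 50" per cent, and then says: "Distribution of a total of 600 kits per setting would enable a precision rate of at least" ±4.0%. For 380 kits it gives ±5.0%. The Study Summary allocates 600 kits to London practice nurses, 600 to London community workers and 380 to Glasgow primary care.

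The section adds that a return rate on either side of 50% can only narrow the interval. It explains that power "increases as the response rate moves away from 50% due to the properties of the binomial distribution". It mentions no design effect, ICC, number of sites or number of kits per site, and these appear nowhere else in the protocol.

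On delivery, Section 6.4 says: "The kits will be distributed by Practice Nurses (PN) in GP clinics in both Glasgow and London". In London, community workers also distribute them. Section 6.2 describes practices in both cities and community organisations in London, all in the plural.

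Secondary objective 7 in Section 5.3 is to "Determine sample size parameters and control population for a phase III trial offering HIV SSK".

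**The concern.** A binomial half-width treats the 600 or 380 kits as independent draws. Here one nurse or worker offers and explains many kits, inside one practice or organisation with its own clientele. The protocol describes ways in which site or distributor could affect return:

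- Section 6.11.2 evaluates training in approaching and persuading people.
- The weekly distributor log (Appendix 11) asks how consistently the taught techniques are used.
- Section 5.7 of the intervention manual lets participants bring the sealed envelope back to the site for posting, which is a direct site-level route to the primary outcome.
- Section 6.2 records practice characteristics for every site.

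If return rates vary between sites within a setting, the estimate carries between-site variance that the formula leaves out, and the stated precision is too favourable. That bears on the study's purpose. Section 14.2 says the intervention manual will carry parameter estimates for a UK-wide phase III trial. For an intervention delivered through sites, the between-site variance is one of those parameters.

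**Working it through.** **Inputs from the protocol.** Return rate p = 0.50; n = 600 and n = 380 per setting (Section 7.1). The confidence level is not stated; two-sided 95% is inferred because it reproduces the figures (90% would give 3.36 and 4.22 points).

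**Step 1: reproduce the stated figures.** Half-width = 1.96 × √(p(1−p)/n).

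- n = 600: 1.96 × √(0.25/600) = 4.00 points
- n = 380: 1.96 × √(0.25/380) = 5.03 points

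These are the stated ±4.0% and ±5.0% after rounding. The Wilson interval gives 3.99 and 5.00. The basis is therefore the independent binomial.

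**Step 2: how much clustering the figures can absorb.** Clustering multiplies the variance by a design effect DE = 1 + (m − 1) × ICC, where m is kits per site (equal sizes). The largest DE compatible with a stated half-width is (stated / binomial)².

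- At 50% return: 1.00 for 600 kits and 0.99 for 380, so no room.
- At 40% or 60% return the binomial half-widths are 3.92 and 4.93. The limits are (4.0/3.92)² ≈ 1.04 and (5.0/4.93)² ≈ 1.03.

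With 30 kits per site, a DE of 1.04 is reached at an ICC of 0.04/29 ≈ 0.0014. With 38 kits per site, 1.03 is reached at 0.03/37 ≈ 0.0008.

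**Step 3: illustrative size.** Numbers of sites and ICCs are assumptions. Half-width = 1.96 × √(0.25 × DE/n), in percentage points, with DE in brackets.

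| Kits | Sites (assumed) | m | ICC 0.01 | ICC 0.02 | ICC 0.05 |
|---|---|---|---|---|---|
| 600 | 20 | 30 | 4.5 (1.29) | 5.0 (1.58) | 6.3 (2.45) |
| 600 | 10 | 60 | 5.0 (1.59) | 5.9 (2.18) | 8.0 (3.95) |
| 380 | 20 | 19 | 5.5 (1.18) | 5.9 (1.36) | 6.9 (1.90) |
| 380 | 10 | 38 | 5.9 (1.37) | 6.6 (1.74) | 8.5 (2.85) |

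Over this grid the range is about ±4.5 to ±8.0 for 600 kits and ±5.5 to ±8.5 for 380.

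**Step 4: fewer sites.** If the community setting used only 5 organisations (m = 120), 600 kits would give ±5.9, ±7.4 and ±10.6 at the three ICCs. All these figures use the normal quantile; a t quantile for few clusters would widen them further.

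**The case against.** **The arithmetic is right.** This stands. Both figures reproduce, and a reader should not take the point as a calculation error. The fault is an unstated assumption behind a figure offered as a guaranteed minimum.

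**The analysis may already allow for clustering.** A reader might infer that the planned confidence intervals will be too narrow. The protocol does not support that. Section 7.2.1 names the outcomes and fixes no interval method, and an SAP not seen here could use clustered intervals. What remains is the precision claim itself, which is made in the protocol.

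**The prognostic model.** A reader might also infer that distributor type and city would look too certain as predictors. Section 7.1 says only that "we will develop prognostic models to examine the extent to which participants with different characteristics achieve the primary outcome", gives age and gender as examples, calls the model exploratory and leaves its parameterisation until before database lock. Nothing there names site-level predictors or rules out a site term.

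**Heterogeneity is already handled by setting.** In part it is: kit numbers are set separately for the three city-by-setting groups, and Section 7.2.1 analyses each setting in each city. That deals with differences between the groups, not between practices or organisations within one.

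**The sites could be treated as fixed.** If inference were limited to the participating sites as fixed strata, the shortfall would vanish. The sites are selected, not sampled, so this reading is possible. It fits poorly with using the estimates to plan a UK-wide trial.

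**The size is unknown and little hangs on it.** The documents do not fix the number of sites or the ICC. At 20 sites and ICC 0.01 the change is from 4.0 to 4.5 points. This is a non-randomised feasibility study, and no test or progression threshold is tied to ±4% or ±5%. That limits the weight of the point but does not make the statement correct.

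**Conclusion.** The point holds as a mis-stated precision under an unstated independence assumption. It follows from the protocol alone that the figures are independent-binomial values, that they are offered as a minimum with no slack at the planning rate, and that kits are delivered within sites. Any positive within-site correlation then makes the precision worse than stated at 50% return, and only a very small one is needed at 40% or 60%.

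The size is illustrative. About ±4.5 to ±8.0 points (600 kits) and ±5.5 to ±8.5 points (380 kits) rest on 10 to 20 equal sites, ICC 0.01 to 0.05, 50% return and a 95% level. Community organisations might be few and large, and four organisations of 150 kits at ICC 0.02 would give DE = 1 + 149 × 0.02 = 3.98 and ±8.0 points, or about ±13 with t on 3 degrees of freedom. Nothing in the protocol says there will be four, so these figures show only how sensitive the claim is to the number of organisations.

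**What to change.** In Section 7.1:

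- Label ±4.0% and ±5.0% as valid under independence only, and state the 95% level.
- State the planned number of practices or organisations per setting, with cluster-adjusted half-widths over ICC 0.01 to 0.05.

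In the analysis section or the SAP:

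- Compute the return-rate interval in each setting with site (practice or organisation) as the cluster and a small-sample correction.
- Report the estimated ICC with its confidence interval as a phase III sample-size parameter under secondary objective 7.

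The data are already collected. The screening and enrolment log (Appendix 3) records the site, and Section 6.8.1 puts the kit number on the recruitment log. Section 6.5.3 ties the kit identifier only to city and setting, so site has to be carried over from the log.

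The cost is a less favourable stated precision and slightly more analysis, with no extra participants or data.

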5.4 Primary Outcome Measure

Our primary outcome is HIV SSK return rate.

[figure not shown]

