5.5 Secondary Outcome Measure

1. Point of delivery outcomes:
 - Acceptability of targeted HIV SSK distribution, including rationales for accepting or refusing the offer of an SSK
 - Acceptability and feasibility of targeted SSK distribution among specified service providers, including utility of protocols for SSK targeting, offers and intervention uptake.
2. Data collection outcomes:
 - Demonstration that intervention models and service provider training and support incorporates sufficient capacity to successfully record the numbers of: people offered SSK, accepting SSK, and returning SSK
 - Feasibility of collecting correct contact details enabling follow-up, reminders and communication of results
3. Pathway to care outcome measures:
 - Proportion of those whose samples are reactive who: a) are informed of results in person and b) who attend for confirmatory testing at an NHS setting of their choice
4. Overarching outcome measures:
 - Cost per person kit distributed and cost per HIV diagnosis per setting
 - Attrition rates and loss to follow up
 - Confirmatory testing, proportion of those receiving an HIV positive diagnoses, and clinical stage at diagnosis
 - Feasibility and sensitivity of outcome measures (testing, behavioural and economic) for a definitive trial.

6. Study Design

This is a prospective, mixed-methods, non-randomised study. The study evaluates the effectiveness of self-sampling for HIV as well as the cost effectiveness of distributing the SSK through GP settings and Community based organisations. Feasibility and acceptability will also be assessed through a process evaluation. Please see the fieldwork schematic diagram in section 6.1 for further information.

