6.9 Sample Collection and Analysis

Participants will be required to self-collect a sample of blood using the TINY vial in the kit provided to them. As indicated in section 6.5.3, there will be instructions including a video link on how to collect the sample. Participants will also be required to complete the form with three unique identifiers (that is initials, date of birth and unique ID number) to enable the sample to be processed at the laboratory. The ID number will be pre-populated on both the lab form and the acceptability questionnaire.

UCLH will be responsible for the following:

1. UCLH via TDL will process samples as soon as they are received.

2. UCLH-TDL will send a CSV file for the study manager of returned samples to enable the manager to send out two reminder texts to participants whose kits have not been returned. This will be sent as an encrypted email.
3. UCLH-TDL will send a CSV file with results for each of the samples returned so that these results can be entered on the database by the study team. This will be sent as an encrypted email.
4. UCLH-TDL will collect the acceptability questionnaires returned with the sample, store them in a locked cabinet and pass these onto the study team.

[figure not shown]

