The Doctors Laboratory (TDL), based at [name], will be contracted by UCLH (University College London Hospitals NHS Foundation Trust) to supply the kits and the processing of the samples for this study. TDL and UCLH already work together on a pathology joint venture, which aims to bring together the best aspects of all partners to ensure quality care for patients and best value for the health economy.

12. Study Committees

A study steering committee was established in August 2014. Study progress and interim analysis of data will be provided to the study steering committee every six months.

13. Finance and Insurance

The study is funded by the NIHR HTA Grant number 12/138/02. We will receive service support costs from the NHS in phase 2 for the NHS sites. The study is sponsored by the University College of London. UCL will provide insurance and indemnity cover for all participants.

University College London holds insurance against claims from participants for harm caused by their participation in this clinical study. Participants may be able to claim compensation if they can prove that UCL has been negligent. However, if this clinical study is being carried out in a hospital, the hospital continues to have a duty of care to the participant of the clinical study. University College London does not accept liability for any breach in the hospital's duty of care, or any negligence on the part of hospital employees. This applies whether the hospital is an NHS Trust or otherwise.

14. Dissemination and outputs

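### The exploratory prognostic model is called pre-specified, but its only deadline is database lock, after kit-return data have reached the study team in a form linkable to baseline items

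*Protocol*

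**What the plan says.** The prognostic model is described in the last paragraph of Protocol section 7.1. On timing it says: "The exact parameterisation of this model will be pre-specified with the project team prior to data base lock". No earlier point is named.

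The same paragraph contains three limits:
- **Status.** "While necessarily exploratory given the primary aim of the study, the prognostic model will help us to develop an understanding of important characteristics".
- **Size.** The number of questions asked of the data is tied to the degrees of freedom, such that "they will not exceed the smaller of the events or non-events divided by 10".
- **Functional form.** Continuous variables such as age are handled by choosing among pre-specified options, "with the switch to a more complex functional form driven by observed significant improvement in model fit as derived by the Akaike Information Criterion".

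The outcome modelled is the primary outcome (section 5.4): "Our primary outcome is HIV SSK return rate". On design, section 6 says: "This is a prospective, mixed-methods, non-randomised study". No blinding is described.

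On data flow, section 6.9 has the laboratory send the study manager a file of returned samples so that reminder texts can go out. It also has the laboratory send a file of results "so that these results can be entered on the database by the study team". Section 6.8.1 says the kit number lets the research team link the two questionnaires to the test result. Section 10.3 says one database holds the quantitative data. Section 12 adds: "Study progress and interim analysis of data will be provided to the study steering committee every six months".

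**The concern.** Specifying a model before database lock protects it only if the people specifying it have not seen the outcome. In a blinded randomised trial, lock usually serves that purpose because treatment allocation is still hidden. Here nothing is hidden. The outcome is whether a kit came back, and the team needs that information as the study runs in order to send reminders.

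If the choice of predictors, and above all how they are grouped, is made after looking at return by participant characteristics, the model's intervals and p-values will be too optimistic. The report could still describe the model as pre-specified. The model is meant to show which characteristics matter for return, in a study whose purpose is to inform a Phase III design, so a chance pattern could carry more weight than it deserves.

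**Working it through.** **1. The plan's own figure.** Section 7.1 gives precision at 50% return as ±4.0% for 600 kits and ±5.0% for 380. Taking a two-sided 95% level (not stated, so assumed), the half-width is 1.96 × √(0.25/n):
- n = 600: 4.00%
- n = 380: 5.03%

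Both reproduce within rounding. This calculation does not involve the prognostic model, so the primary estimate is unaffected by the point.

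**2. Does return reach the team before lock?** Yes. The intervention manual (Appendix 6, section 4.4) says a consenting participant is reminded if the laboratory has no sample within two weeks. The file of returned samples must therefore flow during recruitment. The telephone number needed for the reminder is on the baseline questionnaire (Appendix 4), together with sex, date of birth, last HIV test, partners, country of birth and time in the UK.

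**3. Does an interim report fall before lock?** The study summary gives 4 January to 30 September 2016. That is 270 days, and 270/30.44 = 8.9 months. With reports every six months, at least one should fall inside this period. Its content is not stated.

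**4. Does the size cap close the gap?** The cap is min(p, 1−p) × N/10:

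| Return rate | N = 1580 | N = 600 | N = 380 |
|---|---|---|---|
| 50% | 79 | 30 | 19 |
| 40% or 60% | 63 | 24 | 15 |
| 30% or 70% | 47 | 18 | 11 |

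Compare the parameters needed for the Appendix 4 items at their printed response categories: sex 1, age (linear) 1, last test 5 − 1 = 4, partners 4 − 1 = 3, time in UK 6 − 1 = 5. The total is 14. The three distribution groups (London GP, London community, Glasgow GP) add 2, making 16. Country of birth is free text and must be grouped by someone. In the pooled data the cap is far above this, so it does not restrict which items enter or how they are grouped. In Glasgow alone at 30% or 70% return the cap of 11 is below 14, so something would have to be dropped or merged.

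**5. Does the functional-form rule close it?** Only for continuous variables. It does not reach country of birth or the categorical items.

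**6. Illustrative size.** For k independent null candidates each tested at 5%, the chance of at least one spurious result is 1 − 0.95^k: 23% for k = 5, 26.5% for k = 6, 40% for k = 10 and 64% for k = 20.

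A null simulation used 2000 datasets, 1580 kits, 50% return and six items with univariable tests. It gave 25.9% with one fixed coding per item. With the most striking coding chosen after seeing return, it gave 46.0%. The assumed numbers of codings were age 4, last test 4, partners 2, time in UK 4, region of birth 2 and sex 1. A second simulation with different assumed distributions and groupings gave 28% and 51%.

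The fixed-coding figure is ordinary multiplicity over six items (compare 26.5%) and has nothing to do with timing. Only the increase above it relates to late specification.

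**The case against.** The strongest reply is that lock is an outer limit. A specification made before the first kit comes back complies with section 7.1, and a dated analysis plan, not shown here, may already contain it. This stands in part. A reader might infer that the model will be specified after an interim analysis, and the protocol does not say so. But the protocol chose this deadline itself, and the deadline allows late specification, so the point is not simply detail left to another document.

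A reader might also infer that the team choosing predictors will have watched return by age, gender, setting and testing history for months. The documents do not support that. The files go to the study manager and study team for reminders and data entry. Linkage is possible, but no tabulation by covariate is described. The interim report goes to the steering committee and its content is not given.

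Third, the model is labelled exploratory, its size is capped, and its functional forms come from a pre-specified menu. All three stand and they limit the harm. None of them governs when predictors and groupings are fixed.

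Fourth, the simulation is not the planned analysis. Section 7.1 plans no p-value screening, several items already have printed categories, and the pooled cap lets every item enter in full, so there is little pressure to select. This stands: 46% is a worst case, not an expected error rate.

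**Conclusion.** The point holds in limited form. The stated deadline does not by itself deliver pre-specification, because a model fixed with sight of return by covariate would comply with it. The documents show that this is possible; they do not show that it is planned or likely.

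The consequence is possible optimism in a secondary, exploratory model. The return-rate estimate, its precision and the sample size do not change. The rise from about 26% to 46% (28% to 51% under the other assumed groupings) is an upper illustration. It assumes no true predictors, univariable tests at 5%, invented alternative codings, and deliberate choice of the most striking coding for every item.

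The conclusion itself rests on three things: no earlier deadline being set elsewhere, the interim schedule being kept over the 8.9 months, and lock coming after recruitment ends.

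**What to change.** In section 7.1, replace the database-lock deadline with: before any return data are linked to or tabulated by participant characteristics, and at the latest before the first interim report. Use of return files to send reminders and give results can continue unchanged.

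The specification should be dated and should list the candidate predictors (baseline items, setting and city) with their coding, including the grouping of country of birth, in priority order. Any later change should be labelled post hoc.

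Keep the cap at the observed smaller of events or non-events divided by 10. It needs only the overall return count, which says nothing about which predictors fit, and the priority order settles what is dropped if the cap bites. Setting the degrees of freedom from the planning rate of 50% would be a step backwards: with 1580 kits it would allow 79 parameters where the protocol's own rule allows 47 at 30% or 70% return.

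The cost is small. A decision that is already planned is brought forward, using variables the study already records. No sample size, procedure or clinical step changes.
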